8.5.2. Presentation of Pharmacokinetic Data

All PK concentrations and parameters will be listed.

Summary tables, arithmetic mean (+ standard deviation [SD]) figures, overlaying individual figures, and individual figures by treatment and time postdose will be provided for plasma PK concentrations. All PK concentration figures will be produced on both linear-linear and linear-logarithmic scales, with the exception of figures across all days, which will be produced on the linear-linear scale only. The +SD bars will only be displayed on the linear-linear scale.

Summary tables by treatment will be provided for all PK parameters, with the exception of diagnostic regression-related PK parameters. Summary statistics (n, Mean, SD, CV, minimum, median, maximum, geometric mean [Geom Mean] and geometric CV [Geom CV] will be calculated for plasma and urine LOXO-305 PK parameters. Excluded subjects will be listed in the PK parameter tables, but will be excluded from the statistical analysis and summary statistics and noted as such in the tables.

A subject may be excluded from the PK summary statistics and statistical analysis if the subject has an AE of vomiting that occurs at or before 2 times the median t_{max} .

Individual concentrations deemed to be anomalous will be flagged in the listings and excluded from the summary statistics.

For plasma PK concentration data the following rules will apply:

- Values that are BLQ will be set to 0 for the calculation of summary statistics.
- Arithmetic mean or median values that are BLQ will be presented as 0.
- If any BLQ results (treated as 0) are in a series of summarized data, geometric mean and coefficient of variation (CV) of geometric mean will be reported as not calculated (NC).

Urine concentration data will be listed only.

For PK parameters the following rule will apply:

• For the calculation of summary statistics of PK parameters, all not reported (NR) and NC values in a data series will be set to missing.

• The AUC values will be set to NC if they have been calculated using fewer than 3 concentrations, and/or 3 concentrations if the last is C_{max}.

• Geometric mean and CV will not be calculated for t_{max}.

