1.3. Potential for Drug-drug Interactions

LOXO-305 showed no detectable inhibition (IC₅₀ > 60 μ M) of CYP1A2, CYP2B6, CYP2C19, and CYP2D6, and weak inhibition of CYP2C8, CYP2C9, and CYP3A4 in human liver microsomes. After pre-incubation of microsomes with LOXO-305 and nicotinamide adenine dinucleotide phosphate prior to addition of CYP450 probe substrate, the CYP3A4 inhibitory potency of LOXO-305 was increased, suggesting the potential for time-dependent inhibition of CYP3A4. Further kinetic evaluation confirmed that LOXO-305 is a time-dependent inhibitor of CYP3A4.

In an in vitro hepatocyte assay, LOXO-305 induced messenger RNA (mRNA) for CYP3A4, CYP3A5, CYP2B6, and CYP2C19. For both CYP2B6 and CYP2C19, an increase in activity was seen. For CYP3A4, LOXO-305 did not cause an increase in activity, likely due to concurrent inhibition of CYP3A4 by LOXO-305. LOXO-305 caused a decrease in mRNA for CYP1A2 but did not lead to a reduction of CYP1A2 activity. In the study, CYP2D6, CYP2C8, and CYP2C9 mRNA were not induced.

In vitro LOXO-305 inhibited P-glycoprotein (P-gp), breast cancer resistance protein (BCRP), multidrug and toxin extrusion protein (MATE) 1, and MATE2K. LOXO-305 did not inhibit organic anion transporter (OAT) 1 and weakly inhibited organic anion transporting polypeptide (OATP)1B1, OATP1B3, organic cation transporter (OCT) 1, OCT2, OAT3, and bile salt exporter pump (BSEP).

LOXO-305 is a substrate of P-gp and BCRP. It is not a substrate of the hepatic transporters OCT1, OATP1B1, OATP1B3, or BSEP.

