3.3. Selection of Doses in the Study

3.3.1. LOXO-305

Multiple oral doses of 200 mg LOXO-305 QD will be administered on Days 8 through Day 16 to achieve LOXO-305 steady state, ensuring the maximal effect of LOXO-305 when the effect on the PK of digoxin is determined on Day 16. While doses of 25 mg QD to 300 mg QD have been evaluated, LOXO-305 200 mg given QD has been chosen as the RP2D for the ongoing global Phase 1/2 first-in-human study, LOXO-BTK-18001 in patients with previously treated CLL/SLL or NHL. The available data demonstrate that LOXO-305 appears safe and well tolerated at these doses. At all evaluated doses, no dose-limiting toxicities have been identified in humans.¹

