3. STUDY ENDPOINTS

3.1. Primary Endpoints

The following PK parameters will be calculated whenever possible, based on the plasma concentrations of digoxin and LOXO-305 (as appropriate):

- area under the concentration-time curve from hour 0 to the last measurable concentration (AUC_{0-t})
- area under the concentration-time curve over a dosing interval (AUC_{tau})
- apparent systemic clearance (CL/F)
- maximum observed plasma concentration (C_{max})
- time to maximum observed plasma concentration (t_{max})
- mean residence time based on AUC_{0-t} (MRT_{last})

The following PK parameters will be calculated whenever possible, based on the urine concentrations of digoxin:

- amount excreted in urine per sampling interval (Ae)
- percentage of dose excreted in urine per sampling interval (t_1-t_2) , where $\%f_{eu} = 100$ $(A_{eu}/dose)$
- renal clearance (CL_r)

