6. STUDY TREATMENTS

The study treatment names and ordering to be used in the TFLs are presented in Table 1.

Table 1: Presentation of Study Treatments in Safety TFLs

Study Treatment	Order in TFLs
0.25 mg Digoxin Alone	1
200 mg LOXO-305 QD + 0.25 mg digoxin QD	2

OD = once daily; TFL = table, figure, and listing.

All TFLs will be based on actual treatments.

Table 2 shows a list of the PK treatment labels and ordering that will be used in the TFLs.

Table 2: Pharmacokinetic Treatment Labels

Study Treatment Labels	Order in TFLs
0.25 mg Digoxin Alone	1
200 mg LOXO-305 Once + 0.25 mg digoxin QD	2
200 mg LOXO-305 QD + 0.25 mg digoxin QD	3

QD = once daily; TFL = table, figure, and listing.

The study treatment sequence names and ordering to be used in the TFLs are presented in Table 3.

Table 3. Presentation of Study Treatment Sequences in TFLs

Study Treatment Sequence	Order in TFLs
0.25 mg Digoxin BID (D1) / 0.25 mg Digoxin QD (D2-7) / 200 mg LOXO-305 QD + 0.25 mg digoxin QD (D8-D16)	1

BID = twice daily; QD = once daily; TFL = table, figure, and listing.

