8.5. Pharmacokinetic Assessments

8.5.1. Pharmacokinetic Analysis

The following plasma PK parameters will be determined where possible from the plasma concentrations of LOXO-305 and digoxin using noncompartmental methods in validated software program Phoenix WinNonlin (Certara, Version 8.1 or higher):

Parameter	Unitsa	Definition
$\mathrm{AUC}_{0\text{-t}}$	h*ng/mL	area under the concentration-time curve from hour 0 to the last measurable concentration $(t_{last})^b$
$\mathrm{AUC}_{\mathrm{tau}}$	h*ng/mL	area under the concentration-time curve over a dosing interval ^b (tau=24 hours)
C_{max}	ng/mL	maximum observed plasma concentration
t_{max}	Н	time to maximum observed plasma concentration
CL/F	L/h	apparent systemic clearance
$MRT_{last} \\$	Н	mean residence time (based on AUC _{0-t})
AR_{AUC}	NA	accumulation ratio base on AUCtau (LOXO-305 only)

NA Not applicable

For each subject, the following urine PK parameters will be calculated, whenever possible, based on the urine concentrations of digoxin:

Parameter	Unitsa	Definition	
Ae	mg	amount excreted in urine per sampling interval (t1-t2)	
CL_R	L/h	renal clearance	

^a Units are based on concentration units (provided by the bioanalytical lab or preferred units for presentation of PK parameters) and dose units used in the study.

^b Area under the concentration-time curve will be calculated using the linear trapezoidal rule for increasing and decreasing concentrations

%feu	%	percentage of dose excreted in urine per sampling interval (t1-t2),
		where CCI

^a Units are based on concentration units (provided by the bioanalytical lab or preferred units for presentation of PK parameters) and dose units used in the study.

Additional PK parameters may be determined where appropriate, e.g. terminal elimination half-life $(t_{1/2})$ after last dose (Day 16) with sample collections up to 96 hours postdose.

The PK analysis will be carried out where possible using actual blood sampling times postdose. If an actual time is missing, the sample concentration result will be treated as missing unless there is scientific justification to include the result using the nominal time.

The parameters C_{max} and t_{max} will be obtained directly from the concentration-time profiles. If C_{max} occurs at more than 1 timepoint, t_{max} will be assigned to the first occurrence of C_{max} .

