8.5.3. Pharmacokinetic Statistical Methodology

A statistical analysis will be conducted to investigate the drug-drug interaction on the PK of the following comparisons:

Plasma PK only

• Multiple doses of digoxin coadministered with a single dose of LOXO-305 versus multiple doses of digoxin alone.

Plasma and urine PK

• Multiple doses of digoxin coadministered with multiple doses of LOXO-305 versus multiple doses of digoxin alone.

The natural log-transformed⁴ PK parameters (AUC_{0-t}, AUC_{tau}, C_{max},Ae_{0-x h} and CL_R) will be analyzed using a mixed effect model.⁵ The model will include actual treatment as a fixed effect, and subject as a random effect.

For each PK parameter separately, the least squares mean (LSM) for each treatment, difference in LSMs between the test and reference treatments, and corresponding 90% confidence interval (CI) will be calculated; these values will then be exponentiated to give the geometric least squares mean, geometric mean ratios, and corresponding 90% CI.

Additionally, the pooled estimate (across all treatments) of the within-subject CV will be calculated, and residual plots will be produced to assess the adequacy of the model(s) fitted.

An example of the SAS code that will be used are as follows:

Mixed Model Analysis

```
proc mixed data = <data in>;
  by parcat1n parcat1 pkday paramn param;
  class trtan usubjid;
  model lpk = trtan / cl residual ddfm = kr2;
  lsmeans trtan / cl pdiff = control('1') alpha = 0.1;
  random intercept / subject = usubjid;
  ods output lsmeans = <data out>;
  ods output diffs = <data out>;
  ods output covparms = <data out>;
```

run;

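### Does the SAP commit the study to a first-dose (Day 8) LOXO-305 CL/F that is not a clearance?

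*SAP*

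**What the plan says.** SAP 3.1 lists "apparent systemic clearance (CL/F") among the primary endpoints for digoxin and LOXO-305, qualified by whether calculation is possible and appropriate. SAP 8.5.1 repeats it with a unit and a name only. The plasma AUCs listed there are AUC0-t and AUCtau, with tau equal to 24 h; AUC0-inf is not listed. A terminal half-life is an optional extra, and its example is "after last dose (Day 16) with sample collections up to 96 hours postdose".

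Three other items bring Day 8 into view:

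- SAP 8.5.2 states "Summary tables by treatment will be provided for all PK parameters, with the exception of diagnostic regression-related PK parameters".
- Table 2 in SAP 6 has "200 mg LOXO-305 Once + 0.25 mg digoxin QD" as a separate PK treatment.
- SAP 8.5.1 lists an "accumulation ratio base on AUCtau (LOXO-305 only"), which needs an AUCtau after the first LOXO-305 dose.

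SAP 8.5.2 also sets parameter values that are not reported or not calculated to missing before summarising.

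The mixed model in SAP 8.5.3 covers AUC0-t, AUCtau, Cmax, cumulative urinary excretion and renal clearance. CL/F is not in it. One of its two contrasts is "Multiple doses of digoxin coadministered with a single dose of LOXO-305 versus multiple doses of digoxin alone". Protocol 3.3.1 explains the repeated LOXO-305 dosing as "ensuring the maximal effect of LOXO-305 when the effect on the PK of digoxin is determined on Day 16".

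**The concern.** CL/F equals dose over AUC only when the AUC is AUC0-inf after a single dose or AUCtau at steady state. After the first LOXO-305 dose, a 24-hour AUC is neither. A programmer who applied one formula to every PK treatment would fill a Day 8 LOXO-305 CL/F column with values that are too high, and clearance would appear to fall by Day 16.

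That could mislead. Protocol 1.3 says "Further kinetic evaluation confirmed that LOXO-305 is a time-dependent inhibitor of CYP3A4", and Protocol 1.2 names CYP3A4 as the main CYP enzyme metabolising LOXO-305. A reader could take a pure accumulation artefact for LOXO-305 inhibiting its own metabolism, under the second primary objective (the PK of LOXO-305).

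A related worry concerns digoxin. With a half-life of 1.5 to 2 days, much of the Day 8 exposure comes from doses given before LOXO-305. A small Day 8/Day 7 ratio might be read as no acute P-gp effect, or the difference between Day 8 and Day 16 as a growing interaction.

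**Working it through.** The documents state no CL/F value or accumulation ratio, so there is no plan figure to reproduce. The size of the possible error follows from these inputs:

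- tau = 24 h (SAP 8.5.1 and SAP 10).
- LOXO-305 half-life h of about 20 h (Protocol 1.4.2). It comes from patients sampled over 0 to 8 h, with the 24 h value imputed from predose. The range 15 to 25 h is my assumption.
- LOXO-305 on Days 8 to 16, so Day 16 is the ninth dose.
- One compartment, constant clearance.

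**LOXO-305, Day 8.** First-dose AUC0-24/AUC0-inf = 1 − 2^(−24/h). At 20 h this is 1 − 2^(−1.2) = 0.565. Dose/AUC0-24 is then 1/0.565 = 1.77 times the true clearance, or 77% too high. At 15 h the fraction is 0.670 (49% too high); at 25 h it is 0.486 (106% too high). First-order absorption with tmax at 2 h moves these to 51%, 79% and 109% for 15, 20 and 25 h.

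**LOXO-305, Day 16.** The ninth-dose AUCtau as a fraction of steady state is 1 − 2^(−9×24/h): 0.99995, 0.9994 and 0.9975 at 15, 20 and 25 h. Dose/AUCtau is therefore within about 0.3% of true clearance.

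**Apparent fall if both days were tabulated.** Accumulation ratio = 0.9994/0.565 = 1.77 at 20 h, so the apparent fall is 1 − 1/1.77 = 44% (33% at 15 h, 51% at 25 h). This is the accumulation ratio in another form.

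**Could Day 8 give a sound value another way?** It would need extrapolation to AUC0-inf, which is not planned. The Day 9 dose limits a Day 8 profile to about 24 h, or 24/20 = 1.2 half-lives, while SAP 8.5.1.1 prefers a span of at least 2.

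**Digoxin.** One-compartment superposition of doses at 0 and 12 h, then daily, with half-life 36/48 h (1.5 to 2 days, Protocol 1.6):

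- No interaction. Day 7 AUCtau as a fraction of steady state = 1 − 2^(−168/h) + 2^(−132/h) − 2^(−156/h) = 0.990/0.955. Shifting each time by 24 h gives 0.994/0.968 for Day 8. Dose/AUCtau is thus 1.0%/4.7% too high on Day 7 and 0.6%/3.3% too high on Day 8. Day 8 is slightly the better of the two.
- Assumed 1.5-fold absorption increase from Day 8. The Day 8 dose adds 0.5 × (1 − 2^(−24/h)) = 0.185/0.146. Day 8/Day 7 = (0.994 + 0.185)/0.990 = 1.19 and (0.968 + 0.146)/0.955 = 1.17. Day 16/Day 7 is 1.51/1.55.

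The Day 8 ratio is therefore well below the Day 16 ratio under such an effect, as expected for a first day of coadministration. The 1.5-fold effect is illustrative; the documents give no expected size.

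**The case for a change.** The strongest case for a change is that CL/F is a primary endpoint and should not rest on convention. The SAP restricts other items when it wants to: the accumulation ratio is for LOXO-305 only, and the single-dose contrast is for plasma only. CL/F carries no such limit, and dose over a 24-hour AUC can always be computed on Day 8, so the wording about possibility would not by itself stop anyone. One sentence would close the gap.

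What stands is that the SAP omits the denominator and the day. What does not follow is that it plans a biased number. Dose over a first-dose 24-hour AUC appears nowhere in the documents and has to be supplied by the reader. The SAP asks for a clearance, and on Day 8 the listed AUCs do not yield one for LOXO-305, so leaving that cell uncalculated is the reading consistent with the text. Whether the column exists cannot be checked: the sampling times are redacted, and the table layouts are in a separate shells document.

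The change would also gain little. AUCtau on both days and the accumulation ratio would still show the same rise of about 1.77-fold. Real inhibition by LOXO-305 of its own metabolism would raise that ratio too, so blanking one CL/F column would not separate the two explanations.

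On digoxin, the Day 8/Day 7 ratio is a correct measure of the change in total exposure on that day. The contrast is named for a single LOXO-305 dose, and the protocol assigns the maximal effect to Day 16. Further caveats are a matter for the discussion in the report.

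**Conclusion.** No change is needed. The SAP leaves the CL/F denominator and day unstated, and a pharmacokineticist can fill this correctly within the text by using dose over AUCtau at steady state and giving no LOXO-305 value for Day 8.

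The 77% overstatement (49% to 106% over the assumed half-lives) and the 44% apparent fall (33% to 51%) would arise only if someone applied the steady-state formula to the first dose. They rest on one-compartment kinetics, constant clearance and an approximate, partly imputed patient half-life.

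Even then, only a descriptive table would be affected. The digoxin ratios for AUC and Cmax, their 90% confidence intervals and the urine comparisons do not use CL/F. The digoxin Day 8 contrast contains no error.

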8.5.3. Pharmacokinetic Statistical Methodology

A statistical analysis will be conducted to investigate the drug-drug interaction on the PK of the following comparisons:

Plasma PK only

• Multiple doses of digoxin coadministered with a single dose of LOXO-305 versus multiple doses of digoxin alone.

Plasma and urine PK

• Multiple doses of digoxin coadministered with multiple doses of LOXO-305 versus multiple doses of digoxin alone.

The natural log-transformed⁴ PK parameters (AUC_{0-t}, AUC_{tau}, C_{max},Ae_{0-x h} and CL_R) will be analyzed using a mixed effect model.⁵ The model will include actual treatment as a fixed effect, and subject as a random effect.

For each PK parameter separately, the least squares mean (LSM) for each treatment, difference in LSMs between the test and reference treatments, and corresponding 90% confidence interval (CI) will be calculated; these values will then be exponentiated to give the geometric least squares mean, geometric mean ratios, and corresponding 90% CI.

Additionally, the pooled estimate (across all treatments) of the within-subject CV will be calculated, and residual plots will be produced to assess the adequacy of the model(s) fitted.

An example of the SAS code that will be used are as follows:

Mixed Model Analysis

```
proc mixed data = <data in>;
  by parcat1n parcat1 pkday paramn param;
  class trtan usubjid;
  model lpk = trtan / cl residual ddfm = kr2;
  lsmeans trtan / cl pdiff = control('1') alpha = 0.1;
  random intercept / subject = usubjid;
  ods output lsmeans = <data out>;
  ods output diffs = <data out>;
  ods output covparms = <data out>;
```

run;

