1.6. Risk Assessment

Subjects in the current study will not receive any health benefit (beyond that of an assessment of their medical status) from participating in the study. The risks of participation are primarily those associated with adverse reactions to the study treatments, although there may

also be some discomfort from collection of blood samples and other study procedures. The dose of LOXO-305 administered in this study is not anticipated to induce any potential risk to subjects participating in this study as the dose does not exceed the highest dose safely administered in first-in-human study or healthy volunteer studies. More information about the known and expected benefits, risks, and reasonably anticipated AEs associated with LOXO-305 may be found in the IB.

There is a potential risk that multiple doses of LOXO-305 may lead to decreases in white blood cells including neutrophils, lymphocytes, monocytes, and eosinophils. Therefore, to mitigate any potential immunosuppressive risks during the ongoing SARS-CoV-2 (COVID-19) pandemic, subjects will remain in the Clinical Research Unit (CRU) for 96 hours postdose (Day 20) to allow for LOXO-305 elimination. In addition, subject's hematology laboratory results will be reviewed prior to discharge from the CRU.

Digoxin is a natural cardiac glycoside indicated for the treatment of congestive heart failure that may also be used to treat atrial fibrillation. Digoxin has a narrow therapeutic window, and clinical toxicity can occur, particularly at plasma levels above the normal therapeutic range. Despite its narrow therapeutic range, digoxin is often used as a probe substrate for P-gp in drug interaction studies as it is not metabolized by CYP450 enzymes; gut bacteria have been shown to inactivate digoxin. Digoxin is a probe substrate for P-gp as listed by the FDA. The half-life of digoxin is approximately 1.5 to 2 days. The dose of digoxin chosen for this study, 0.25 mg, is well characterized. Adverse effects caused by digoxin toxicity are well characterized and easily monitored in the clinical setting, and these effects can be treated if required. To monitor for safety, serum digoxin levels will be measured daily (Days 7 through 15) in a clinical safety laboratory assay. These values are for safety only and will not be used to calculate the PK of digoxin.

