3. INVESTIGATIONAL PLAN

3.1. Overall Study Design and Plan

This is a Phase 1, open-label, fixed-sequence DDI study to investigate the effect of single and multiple oral doses of LOXO-305 on the PK of multiple oral doses of digoxin (P-gp substrate) in healthy subjects.

On Day 1, subjects will be administered oral 0.25 mg digoxin BID (loading dose), once in the morning and evening. Subjects will be fasted for at least 2 hours predose and 1-hour postdose for the morning and evening dose.

On Days 2 through 16, oral doses of 0.25 mg digoxin QD will be administered (total of 17 consecutive doses) at the actual time of the Day 1 morning digoxin dose (± 1 hour). On Days 8 through 16 (9 consecutive doses), oral doses of 200 mg LOXO-305 QD will be coadministered with 0.25 mg digoxin QD, at the actual time of the Day 1 morning digoxin dose (± 1 hour). LOXO-305 will be administered first, immediately followed by digoxin. On Days 2, 4 through 6, 9 through 11, 13, and 14, subjects will fast for at least 2 hours predose and 1-hour postdose. On Days 3, 12, and 15 where clinical laboratory evaluations are performed, subjects will fast for at least 8 hours predose and 1-hour postdose. On Days 7, 8, and 16, subjects will be fasted at least 10 hours predose and 2 hours postdose. Blood and urine samples for concentrations of digoxin in plasma and urine and

Blood samples for concentrations of LOXO-305 and digoxin in plasma and

Urine samples for concentrations of digoxin and CCl

Samples collected for the analysis of plasma and urine concentrations of digoxin and for analysis of LOXO-305 in plasma may be stored and analyzed CCl

The schematic of the study design is displayed in Figure 3. The start of the study is defined as the date the first subject who is enrolled in the study signs an Informed Consent Form (ICF). Note that enrolled subjects are defined as those subjects who are assigned to receive a dose of study drug; this definition excludes screen failure subjects. Replacement subjects may be enrolled only if deemed necessary by the Sponsor.

[figure not shown]
Subjects who are determined to be screen failures are permitted to be re-screened if the Investigator (or designee), with agreement from the Sponsor, feels that the subject may meet eligibility criteria upon re-screen. Re-screened subjects will be provided a new subject number.

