3.3.2. Digoxin

The selected dose of digoxin is based on typical doses for this drug when used as an index substrate in DDI studies and is considered to be high enough to provide sufficient plasma concentrations to achieve the objectives of the study. Following the initial loading dose and given a $t_{1/2}$ of approximately 1.5 days, digoxin plasma concentrations would be expected to achieve steady-state by Day 7 in the absence of LOXO-305. Day 7 has therefore been selected for the steady-state digoxin PK sampling and Day 8 has been chosen for the first LOXO-305 coadministration. Subjects may be withdrawn if their trough serum digoxin level exceeds 2.0 ng/mL and/or they exhibit clinically significant signs or symptoms of digoxin toxicity.

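### Digoxin AUC0-t is modelled for Day 16 versus Day 7 with no common end time in the visible text; if Day 16 digoxin sampling runs past 24 h, that one ratio exceeds 1 without any interaction

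*SAP*

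**What the plan says.** SAP 8.5.3 lists two comparisons, each of digoxin with LOXO-305 against digoxin alone, and states that "PK parameters (AUC_{0-t}, AUC_{tau}, C_{max},Ae_{0-x h} and CL_R) will be analyzed using a mixed effect model". Each parameter receives a geometric mean ratio with a 90% CI.

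The days come from the protocol. Section 3.3.2 fixes the reference: "Day 7 has therefore been selected for the steady-state digoxin PK sampling". Section 3.3.1 fixes the multiple-dose test day: "when the effect on the PK of digoxin is determined on Day 16". SAP Section 4 ends digoxin dosing on Day 16.

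SAP 3.1 lists as a primary endpoint "area under the concentration-time curve from hour 0 to the last measurable concentration (AUC_{0-t"). AUCtau, by contrast, has a fixed 24 h interval (SAP 8.5.1). SAP 8.5.1 also allows further parameters where appropriate, giving as its example a half-life "after last dose (Day 16) with sample collections up to 96 hours postdose". That sentence names no analyte.

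The only rule in the visible text that ties quantities to a shared end time is for renal clearance (SAP 8.5.1.3), where urinary amount and AUC must end together within a profile. None is visible for AUC0-t between days.

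**The concern.** A ratio of two AUCs measures a change in exposure only if both cover the same length of time. The Day 7 profile cannot run past about 24 h, because the next digoxin dose is given on Day 8. No dose closes the Day 16 profile. If digoxin is followed for two to four days after the Day 16 dose, the Day 16 AUC0-t includes one to three extra days of a slowly eliminated drug, while Day 7 covers one day. Protocol 1.6 states: "The half-life of digoxin is approximately 1.5 to 2 days". Much of the area therefore lies beyond 24 h.

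At stake is one row of the primary PK table. It could show a rise in digoxin exposure that comes from the time window, next to an AUCtau ratio near 1.

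**Working it through.** The documents give no expected ratio or power figure, so there is none to reproduce. The check is what the Day 16 over Day 7 ratio would be with no interaction.

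**Inputs from the documents**
- Half-life h of 36 to 48 h (Protocol 1.6).
- Two digoxin doses on Day 1, then one daily on Days 2 to 16, 17 in all (SAP Section 6, Table 3; Protocol 5.2).
- Reference Day 7 and test Day 16 (Protocol 3.3.1, 3.3.2); tau of 24 h (SAP 8.5.1).

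**Assumptions, not in the documents**
- Evening dose on Day 1 given 12 h after the morning dose; one-compartment decline with instantaneous input.
- Last measurable Day 16 sample at 48, 72 or 96 h. Only 96 h appears in the visible text, and not specifically for digoxin.

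**Step 1, window factor.** Let x = 2^(−24/h). After the last dose, AUC(0–24n)/AUC(0–24) = 1 + x + … + x^(n−1).
- h = 36: x = 0.630, giving 1.630 (48 h), 2.027 (72 h), 2.277 (96 h).
- h = 48: x = 0.707, giving 1.707, 2.207, 2.561.

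**Step 2, approach to steady state.** The fraction of steady-state AUC0-24 reached on Day m is F(m) = 1 − x^m + (1 − x)·2^(−(24(m−1)−12)/h). The last term is the extra Day 1 dose.
- h = 36: F(7) = 1 − 0.0394 + 0.370 × 0.0787 = 0.990; F(16) = 0.9998; ratio 1.010.
- h = 48: F(7) = 1 − 0.0884 + 0.293 × 0.1487 = 0.955; F(16) = 0.998; ratio 1.045.

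This is the no-interaction AUCtau ratio: 1.01 to 1.05.

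**Step 3, product of the two.**

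| Last Day 16 sample | h = 36 h | h = 48 h |
|---|---|---|
| 24 h | 1.010 | 1.045 |
| 48 h | 1.647 | 1.784 |
| 72 h | 2.047 | 2.306 |
| 96 h | 2.300 | 2.676 |

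**Step 4, sensitivity to an early peak.** Add a fast phase with a 1 h half-life and an intercept 15 times the slow one. With h = 36 and a unit slow intercept, the fast area per dose is 15/ln 2 = 21.64 and the slow steady-state area per interval is 36/ln 2 = 51.94.
- Day 7: 21.64 + 0.990 × 51.94 = 73.05, of which the fast phase is 29.6%.
- Day 16 to 48 h: 21.64 + 1.630 × 51.93 = 106.28; ratio 1.455.
- Day 16 to 96 h: 21.64 + 2.277 × 51.93 = 139.87; ratio 1.915.

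First-order absorption (rate constant 0.5 to 1.0 per h, no early peak) moves the upper ends slightly the other way, to 1.80–1.81 at 48 h and 2.70–2.73 at 96 h.

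**Step 5, would the interval show it?** With 16 subjects, 30 residual df and an assumed within-subject CV, the 90% CI factor is exp(1.697 × √ln(1 + CV²) × √(2/16)): 1.126 at CV 20% and 1.193 at CV 30%. Around 1.455 this gives 1.29 to 1.64 and 1.22 to 1.74. Both exclude 1.

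**Step 6, the other comparison.** The Day 9 dose closes Day 8 at 24 h, so Day 8 versus Day 7 has equal windows (no-interaction ratio 1.004 to 1.014).

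**The case against.** The strongest reply is that the fault depends on text we cannot see. The sampling times are redacted in the protocol's synopsis, Sections 3.1 and 8.3, and the assessment schedule. If nominal digoxin sampling stops at 24 h on Day 16, the schedule itself supplies the common end time. A redacted rule is not a missing rule. Protocol 1.6 also explains the 96 h stay by LOXO-305 elimination, so the late samples may be for LOXO-305 alone. AUC0-t is listed for the two analytes as appropriate, and LOXO-305 could be the reason for keeping it. All of this stands.

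A reader might infer that digoxin is sampled to 96 h from two hints. The protocol's sampling text has "Blood samples for concentrations of LOXO-305 and digoxin in plasma and", naming both drugs in one cut sentence. The SAP's parameter table restricts one item, "accumulation ratio base on AUCtau (LOXO-305 only"), but puts no such limit on the half-life example. Neither hint settles it. Both drugs are given together from Day 8 and both need profiles, so the first sentence would read the same with digoxin ending at 24 h. The half-life sentence is optional, and a missing analyte label does not point to digoxin.

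It is also fair that AUCtau is modelled alongside and gives a like-for-like estimate, and that the lower figures (1.46 and 1.92) need an early peak found nowhere in the documents.

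What the reply does not rescue is the purpose of modelling AUC0-t. Every comparison in SAP 8.5.3 is of digoxin against digoxin alone. AUC0-t therefore either essentially repeats AUCtau, which is the reason SAP Section 10 gives for dropping AUC0-24, or it compares unequal windows. A use for LOXO-305 explains calculating it, not putting it in this model.

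**Conclusion.** Minor and conditional. If digoxin is measurable past 24 h on Day 16, the no-interaction AUC0-t ratio is about 1.65 to 1.78 for a last sample at 48 h and 2.30 to 2.68 at 96 h. These figures rest on the documented half-life and regimen under a one-compartment decline. An assumed early peak of up to about 30% of AUC0-24 lowers them to about 1.46 and 1.92. Late values below quantification would end the profile earlier, lower the ratio further and make it vary by subject. If digoxin stops at 24 h, the window bias is zero.

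The documents do not support saying that the plan will report a false interaction. The condition is unconfirmed, AUCtau, Cmax and Day 8 versus Day 7 are unaffected by the window, and the visible text sets no decision rule on AUC0-t. The interaction estimate is not lost; the harm is at most one misleading primary-endpoint row.

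**What to change.** In SAP 8.5.3, base between-day digoxin AUC inference on AUCtau, or restrict digoxin AUC0-t to 0–24 h on Days 7, 8 and 16. Report any longer Day 16 digoxin AUC0-t descriptively only. Record the change in SAP Section 10 as a departure from Protocol 8.3.2, whose first listed AUC is garbled in the extracted text but is read here as AUC0-t.

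The cost is SAP wording and table shells; no samples or study procedures change. The edit is harmless if digoxin sampling already stops at 24 h.
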